4.2.1.2 Cohorts Description

The dose escalation part will be conducted over five cohorts from a starting cumulative activity of 5 GBq up to a maximum cumulative activity of 15 GBq, fractionated into two administrations of 2.5 GBq and 7.5 GBq respectively.

The size of the cohorts will be three to five treated subjects, to secure a minimum of three evaluable subjects per cohort who completed 2 cycles of treatment. A cohort will be considered as completed once three subjects of the cohort complete Cycle 2 or early discontinue during Cycle 2 (except for cohort 1, see *Proceeding to the Next Cohort* described in Section 4.2.1.4). If a subject replacement is needed to complete the cohort enrolment, see Section 4.7.1.3 for replacement rules.

For safety reasons, the first three subjects of a cohort will be administered sequentially, one week apart to allow a sufficient observation period for any adverse reaction.

4.2.1.3 Dose Escalation Mode

Dose escalation is planned to proceed in two steps, with two different increments for the radioactivity escalation. In the first step, in order to minimise the number of subjects receiving subtherapeutic activity, the inter-cohort radioactivity escalation will be performed by increment of 3 GBq (1.5 GBq per administration), up to the first study drug related treatment-emergent AE (TEAE) (Grade 2 or higher, except hair loss) or until a DLT occurs. Afterwards, the maximum increment will be reduced to 2 GBq (1 GBq per cycle) for all subsequent cohorts if dose escalation is allowed. However, even if no Grade 2 or higher AE are observed up to a cumulative activity of 11 GBq, radioactivity will be increased by 2 GBq (1 GBq per cycle).

Table 5 illustrates the escalation plan based on the escalation scheme defined above. However, if DLTs are reported, a statistical Bayesian modelling approach will be implemented to produce a more precise dose-DLT curve to guide the dose selection (see details in Attachment 5, Section 19.5) and predict an activity not exceeding the MTCA/MTSA that could be tested in the next cohort.

Planned radioactivity Cohort 1 Cohort 2 Cohort 3 Cohort 4 Cohort 5 escalation Cumulative 5 GBq 8 GBq 11 GBq 13 GBq 15 GBq 2.5 GBq/C 4 GBq/C 5.5 GBq/C 6.5 GBq/C 7.5 GBq/C Per cycle

Table 5 Cohorts and Radioactivity Escalation Plan

C=cycle; GBq=gigabecquerel.

Once the dose escalation has been completed, the MTCA level may be repeated in a last cohort (see Section 4.2.1.4 for stopping rules and Section 4.2.1.1 for MTCA definition). If the MTCA is not reached and if limiting organ dose levels are not exceeded at the highest planned activity (2×7.5 GBq) and if no individual withdrawal criteria are met, an additional cohort (Cohort 6) with three administrations at the highest single administration level may be added (3×7.5 GBq).

4.2.1.4 Safety Review Committee

The SRC will review the safety and radiation exposure data and jointly decide with the sponsor whether to proceed with the enrolment of the next cohort dose level and the second dosing cycle within a cohort. For this purpose, the SRC will be composed of all phase I investigators, who have treated at least one subject in the study cohort with study medication, one independent expert, a dosimetry expert evaluating the dosimetry data of the study (from a centralised dosimetry centre) and at least one sponsor representative. Regular meetings will be held. A specific charter will be developed to define roles and responsibilities, as well as the dataset to be reviewed by the SRC and the review timepoints.

[figure not shown]

Figure 2 Flow of Dose Escalation Cohorts and SRC Meetings

A=administration of study compound; EOCT=end of core trial; SRC=Safety Review Committee.

SRC1=Decision on start of next cohort

SRC2=Confirmation or adjustment of A2 in next cohort

Proceeding to the Next Cohort

At the time of radioactivity escalation, the available clinical safety and radiation exposure information will be reviewed and discussed by the SRC to jointly decide with the sponsor if the escalation can proceed as planned.

For each cohort, an SRC meeting will be held after the end of the third subject's Cycle 1. If during that observation period (after the first administration) no DLT occurs and all three subjects can receive the full radioactivity level (RL) as planned for the respective cohort (i.e. all three subjects can receive the second administration), the next cohort can be started with the first administration of the first subject at the earliest 3 weeks after the third subject of the previous cohort has received the second administration. No more than two dose-escalation cohorts will be conducted in parallel (Figure 2). If a DLT occurs after the first administration in cohort n, cohort n+1 will only be started after the second SRC (2nd administration) of the cohort n.

Due to the possible subtherapeutic activity of the lowest dose, the escalation decision to the planned dose of 4 GBq/cycle in Cohort 2 will be taken if only one subject from Cohort 1 has received the second administration without any safety problems at the end of the second cycle (i.e. at Cycle 2 Day 29, see Figure 2).

Proceeding to the Second Administration in a Cohort

For each cohort, a SRC meeting will be held after the end of the third subject's Cycle 2 of the preceding cohort and before the second administration of the first subject in a cohort, (Figure 2) to review all available safety data and radiation exposure from previous cohort(s). The second radioactivity administration will be confirmed based on the rules described in Attachment 5, Section 19.5.

Stopping Rules for Dose Escalation

The MTCA is defined in Section 4.2.1.1.

The radioactivity escalation will be stopped as soon as:

- The MTCA and/or MTSA have been defined with good precision; or
- The maximum planned radioactivity of 15 GBq, fractionated into two administrations separated by 4 weeks, is administered without safety concerns.

Transition from Dose Escalation to Other Study Parts

Upon completion of the phase I dose escalation or upon reaching the MTCA and confirmed jointly by the SRC and the sponsor, and in consideration of the accumulated subject data, cohorts of subjects will be studied to further characterise the safety and efficacy of ¹⁷⁷Lu-3BP-227. In the case of acceptable tolerability and evident antitumour activity across all enrolled subjects in phase I, a phase II basket trial design will be utilised to study the antitumour activity of ¹⁷⁷Lu-3BP-227 in subjects with NTSR1 expressing tumours. However, if the antitumour activity is driven by a certain type of tumour, tumour-specific phase II cohort(s) will be initiated utilising an Optimal Simon's Two Stage design (see Section 4.3).

4.2.2 Dose Expansion

If safety evaluation and dose schedules of ¹⁷⁷Lu-3BP-227 cannot be fully explored during the phase I dose escalation part, a phase I expansion part will serve to accomplish this objective including, but not limited to, schedules of high loading doses followed by fractionated lower doses or evaluation of ¹⁷⁷Lu-3BP-227 in combination with other antitumoral treatments (to be defined). The expansion part will also serve to clarify any uncertainties of antitumour responses.

The number of cohorts and subjects will be determined based on emerging data from the dose escalation part and the modelling and simulation approach, and will be documented as part of a protocol amendment.

4.3 Phase II

Phase II study will be conducted either with a basket design trial or indication-specific cohorts with an Optimal Simon's Two Stage design, according to the scenarios described above.

One, two or three further cohorts may be initiated (subject to results emerging from ongoing preclinical studies and antitumour efficacy seen during dose escalation and amending the current protocol) likely to enrol subjects with GC, ES and/or SCCHN.

- The PDAC cohort will enrol approximately 55 subjects and will investigate whether ¹⁷⁷Lu-3BP-227 attains an ORR superior to a clinically accepted historical threshold of current standard-of-care treatment for subjects with unresectable, locally advanced or metastatic disease.
- The CRC cohort will enrol approximately 70 subjects and will investigate whether ¹⁷⁷Lu-3BP-227 attains an ORR superior to a clinically accepted historical threshold of current standard-of-care for subjects with unresectable, locally advanced or metastatic disease.

The current protocol will be amended at the end of the phase I to document the rationale of the phase II design. In any case, the cumulative activity administered during phase II will not exceed the MTCA determined during phase I.

Sample size calculation for cohorts other than PDAC and CRC will be documented as part of a protocol amendment.

4.4 Study Endpoints

4.4.1 Primary Endpoint

4.4.1.1 Phase I

For the dose escalation, the primary endpoint is MTCA or MACA, if the MTCA is not identified during the dose escalation part. The primary variables used for the MTCA determination will be the incidence of DLTs (as defined in Section 4.7.1.1) and the organ exposure to radiation during two cycles of treatment. The DLT period for the determination of the primary endpoint

starts at the first administration of ¹⁷⁷Lu-3BP-227 to EOCT/ED. Safety evaluation will encompass DLTs, frequency and nature of AEs, abnormal findings from physical examination, vital signs, 12-lead electrocardiogram (ECG), 3-lead ECG Holter, Eastern Cooperative Oncology Group (ECOG) performance status deterioration, clinical laboratory tests (including haematology, blood biochemistry, hormone analysis, urinalysis and pregnancy test) and changes in specific renal safety biomarkers.

In case the phase I dose expansion cohorts are implemented, the primary endpoint will be safety and tolerability measured by the type, severity, expectedness and frequency of AEs.

4.4.1.2 Phase II

The primary endpoint is ORR measured by CT or MRI using RECIST version 1.1. Tumour response assessments are performed every 8 weeks or at the time of occurrence of first signs of clinical progression as determined by the investigator.

4.4.2 Secondary Endpoints

4.4.2.1 Phase I

For biodistribution and dosimetry of ¹⁷⁷Lu-3BP-227, the secondary endpoints are:

- Maximal uptake (%), maximal concentration achieved (C_{max}); time post injection to achieve maximal concentration (T_{max}); AUC at the target lesions, discernible organs and blood; t_{1/2} of activity concentrations in blood;
- Highest absorbed dose, specific absorbed dose to the target lesions (Gy/GBq), specific absorbed dose per organ (Gy/GBq) and cumulative absorbed organ doses (Gy).

For PK of 3BP-227, the secondary endpoints are:

• PK parameters including, but not limited to, C_{max}, AUC, t_{1/2}, CL, V_d, cumulative amount of unchanged drug excreted into the urine (Ae), renal clearance of the drug from plasma (CL_R), as measured in plasma and urine at defined timepoints.

For pharmacodynamics, the secondary endpoints are:

- Objective response rate and DCR, as determined by RECIST version 1.1 in subjects who received IMP;
- Progression-free survival (PFS) and OS rates as determined from start of study treatment until occurrence of event and/or end of observation period;
- Evaluation of metabolic tumour response using PERCIST (version 1.0) or practical PERCIST;
- Changes in serum tumour markers relevant and specific to the underlying tumour disease from baseline to EOCT, which is planned 6 weeks after the second ¹⁷⁷Lu-3BP-227 dose administration.

4.4.2.2 Phase II

The secondary endpoints are:

- Disease control rate, time to progression (TTP), time to response (TTR), duration of response (DOR) as per RECIST version 1.1;
- Qualitative and quantitative changes in tumour-to-background uptake using PERCIST version 1.0;
- Progression-free survival (PFS) and OS as determined from start of study treatment until occurrence of event and/or 6 and 12 months after start of study treatment;
- Changes in serum tumour markers relevant and specific to the underlying tumour disease from baseline to EOCT;

- Changes in health-related quality of life scores from baseline to EOCT measured by validated and disease-specific questionnaires;
- Safety and tolerability measured by the type, severity, expectedness and frequency of AEs;
- For PK, biodistribution and dosimetry, the endpoints will be similar as for phase I.

4.4.3 Exploratory Endpoints

Exploratory endpoints are the same for phase I and II:

- Tumour uptake of ¹⁷⁷Lu-3BP-227 and the correlation with NTSR1 expression on tumour biopsies;
- Tumour microenvironment and other markers of interest (such as NTSR1 expression, Ki67, gene expression and DNA damage) in tumour biopsies taken at baseline, at EOCT visit or at disease progression, whichever occurs earlier;
- Genomic profiling in circulating cfDNA and in germline DNA;
- Gene mutation status in correlation with clinical outcome;
- Specific renal safety biomarkers specific for proximal tubulus toxicity.

4.5 Study Duration

For phase I, the maximum duration of subject participation in the core trial is 21 weeks. However, if, according to the investigator, a subject has clinical benefit, the subject may receive up to four additional cycles after the EOCT, provided they have an acceptable tolerability profile and the organ dose limits are not exceeded. This is at the subject's discretion and must be discussed and agreed upon with the sponsor. The clinical benefit will be defined as CR, PR or stable disease (SD) as per RECIST criteria version 1.1 or based on biochemical responses.

For phase I dose expansion and phase II, the study duration will be refined in light of phase I results and recommended treatment regimen (doses and intervals).

In all cases, a long-term follow-up period will start after the EOCT, ED or EOAC visit and subjects will be followed up every three months (±2 weeks) until lost to follow-up, withdrawal of consent, death or a maximum of 5 years, whichever occurs first.

4.6 Randomisation and Blinding

4.6.1 Method of Randomisation

4.6.1.1 Subject Unique Identifier

At screening, potential subjects will be allocated an 11-digit subject number consisting of:

- The country code (three digits);
- The centre number (three digits);
- The sequential order of entry of the subject at the centre (five digits).

4.6.1.2 Randomisation Number

Not applicable for phase I, as this is not a randomised study.

For the phase II, the protocol could be amended to include randomisation.

4.6.2 Blinding

Not applicable, this is an open-label study.

4.6.3 Code-break

Not applicable, this is not a blinded study.

4.7 Discontinuation Rules

4.7.1 Individual Discontinuation Rules

In accordance with the Declaration of Helsinki and the applicable country's regulations, each subject is free to withdraw from the study at any time and for any reason without prejudice to their future medical care by the investigator at the institution.

The investigator will be responsible for monitoring subject compliance. A subject can be withdrawn from the study at any time if the investigator or the sponsor determines that the subject is not in compliance with the study protocol.

The investigator has the right to withdraw a subject from the study in the event of concurrent illness, AEs, or other reasons concerning the health or well-being of the subject, or in the case of lack of cooperation.

If any of the following occur, no further treatment will be administered:

- life-threatening toxicities outside of the DLT reporting period
- subject withdraws their consent to further treatment;
- cumulative kidney dose exceeds 23 Gy;
- cumulative bone marrow dose exceeds 2 Gy, as determined by dosimetry of peripheral blood samples and imaging;
- cumulative liver dose exceeds 30 Gy;
- occurrence of a DLT for phase I dose escalation only (see Section 4.7.1.1).

All cases of discontinuation will be discussed between the investigator and the sponsor.

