4.7.1.1 Definition of Dose Limiting Toxicity (Dose Escalation)

The DLTs are defined for any of the following IMP-related AEs according to National Cancer Institute - Common Terminology Criteria for Adverse Events (NCI-CTCAE) scale version 5.0 [31], that occur during the defined DLT assessment period (from the first administration of ¹⁷⁷Lu-3BP-227 to EOCT/ED):

- Grade 4 neutropenia for seven or more consecutive days;
- Febrile neutropenia or neutropenic infection (defined as a documented infection with neutrophil count decreased Grade 3 or 4);
- Grade 3 or 4 thrombocytopenia (platelet count decreased) with clinically meaningful bleeding (i.e. requiring urgent hospitalisation or transfusion to manage the bleeding);
- Grade 4 thrombocytopenia for seven or more consecutive days;
- Any Grade 3 anaemia (Hb<8.0 g/dL; transfusion indicated) or Grade 4 anaemia (life-threatening consequences; urgent intervention indicated);
- Any Grade 3 or higher laboratory abnormalities on aspartate aminotransferase/alanine aminotransferase (AST/ALT) with accompanying Grade 2 or higher bilirubin (Hy's law);
- any Grade 3 or higher renal injury/toxicity (estimated glomerular filtration rate (eGFR) <30 mL/min/1.73 m²);
- Any Grade 3 or higher GI AE, not resolved to Grade ≤2 within 48 hours despite optimal adequate medical management, with the following specifications:
 - Grade 3 nausea, vomiting (inadequate oral caloric or fluid intake; tube feeding, total parenteral nutrition or hospitalisation indicated)
 - Grade 3 diarrhoea (increase of ≥7 stools per day over baseline; hospitalisation indicated; severe increase in ostomy output compared to baseline; limiting self-care activities of daily living (ADL)) or Grade 4 diarrhoea (life-threatening consequences; urgent intervention indicated)

- Grade 3 constipation (obstipation with manual evacuation indicated; limiting self-care ADL) or Grade 4 constipation (life-threatening consequences; urgent intervention indicated);
- Any toxicity related to ¹⁷⁷Lu-3BP-227 resulting in a treatment delay of more than four weeks due to either delayed recovery to baseline or resolution of any AE to Grade ≤2 (with the exception of alopecia and lymphopenia).
- Grade 5 toxicity (death)

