12.2.8 Interim Analysis/Safety Review Committee

During the dose escalation part and before each decision on further dose escalation, safety and dose limit organ exposure data will be summarised and presented to the SRC. This SRC will be set-up for the dose escalation decisions (after the end of the third subject's Cycle 1) and second dosing cycle (after the end of the third subject's Cycle 2).

At the time of SRC meeting, all cumulative available information will be reviewed.

A continual reassessment method (CRM) in conjunction with a Bayesian approach modelling of DLT rates and radiation exposure to target organs may be performed during the planned review meetings to generate additional relevant information for the adaptive dose selection decisions. PK and pharmacodynamic data may be also incorporated in the model. The SRC will review all available data and make the final decision as to dose escalation, de-escalation, or cohort expansion during the adaptive dose-escalation phase. This group will also determine when to implement predefined stopping rules.

An interim analysis of the escalation cohort data may be done when the MTCA or MACA have been determined.

A specific charter will be developed to define roles and responsibilities, as well as the data set to be reviewed by the SRC.

Full analysis will be performed on the entire dataset at the EOCT and at the end of the long-term follow-up.

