During the study, the target organ exposure will be monitored after each dose and doses may be adapted if the exposure exceeds organ-specific maximum acceptability limits. As such, if the predicted MTCA exceeds the maximum acceptability limits for target organ exposure, the maximum radioactivity dose will be used instead. This feature was not considered in the simulation study, where it was assumed that a cumulative dose up to 15 GBq would induce an acceptable organ exposure.

Prior distributions were elicited based on historical knowledge about the placebo DLT rate and the MTSA target. The following prior distributions are used in the trial:

$$p_0 \sim beta(a=1,b=9)$$
,
MTSA $\sim gamma$ (shape = 4, rate = 0.5),
and

 $\beta \sim normal \ (\mu = 0, sd = 0.25).$

Based on these distributions, 20 dose-DLT curves from the prior distribution were simulated after Dose 1 (black) and after Dose 1 and 2 (red) (see Figure 3). The prior probability distributions for the MTSA is summarised in Table 10. The prior probability distributions for the MTCA is summarised in Table 11

[figure not shown]

Figure 3 40 Random Observations (Curves) from the Prior Distribution

Table 10 Prior Probability Distribution of MTSA

Dose range for Cycle 1	Prior MTSA probability
2.5 GBq	5.2%
2.5 to 5 GBq	20.6%
5 to 7.5 GBq	28.6%
>7.5 GBq	45.6%

MTSA=Maximum tolerated single activity.

Table 11 Prior Probability Distribution of MTCA

Dose range (cumulative)	Prior MTCA probability
≤5 GBq	32.5%
5 to 10 GBq	24.6%
10 to 15 GBq	15.7%
>15 GBq	27.2%

MTCA= Maximum tolerated cumulative activity.

Given any set of data, the prior distribution can be updated, yielding a posterior distribution of the parameters. From this posterior distribution many different quantities of relevance can be calculated:

- $E(p|d_1, d_2)$ =Posterior mean probability of DLT for Cycle 1 dose d_1 and Cycle 2 dose d_2 .
- TS_d=(tolerable) Probability that the DLT rate is below 0.33, $Pr(p \le 0.33 | d,0)$, for a Cycle 1 dose d (d₂=0).
- QS_d=Probability of Cycle 1 dose d being the maximum dose where $E(p|d,0) \le 0.33$.
- TC_d=(tolerable) Probability that the DLT rate is below 0.33, $Pr(p \le 0.33 | d/2,d/2)$, for a cumulative dose d (d₁=d₂=d/2).
- QC_d=Probability of cumulative dose d being the maximum dose where E(p|d/2,d/2) <0.33.

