 - (a) if there are two DLTs out of three, three DLTs out of five, or three DTLs out of six subjects receiving a single or cumulative dose, d must be lower than or equal to that dose;
 - (b) if there are three DLTs out of three, or at least three DLTs out of four, or at least four DLTs out of five, or at least four DLTs out of six subjects receiving a single or cumulative dose, d must be lower than that dose;
 - (c) dose d must be at most 1 GBq larger than the maximum Cycle 1 dose tested previously.

Repeat steps 2 and 3 again, assigning the subjects/cohort to this dose. Terminate study enrolment when any of the following stopping rules happen:

- A the MTSA is precisely estimated: CV (MTSA) calculated as the inter-quartile range over the median is lower than 30%;
- B maximum possible dose (7.5 GBq) is safe: TS_{7.5}>80% and d₁=7.5 GBq administered;
- C minimum dose tested (2.5 GBq) is toxic: TS_{2.5} <20%;
- D total sample size for next dose is already ≥ 6 .

The MTSA will be declared to be found when study stops for criteria A or D.

Individual dosing decision for the second treatment cycle will be done as follows:

- Subject will be eligible for Cycle 2 only if subject had no DLT during Cycle 1. Subjects with DLTs in Cycle 1 will be discontinued and replaced with a maximum of two replacements.
- The same fractional dose as in Cycle 1 will be repeated during Cycle 2 ($d_2=d_1$), if the dose having the largest probability to be the MTCA is larger than 2 x d_1 .
- The fractional dose for Cycle 2 will be decreased to d₂=MTCA-d₁ dose, if the predicted cumulative exposure after Cycle 2 is above the MTCA target. In this situation, the cumulative exposure after two cycles should not exceed the MTCA.

The study will be terminated when all cohorts have ended the study, as defined above.

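### Inside the DLT window, a related life-threatening event that is off the DLT list and recovers within the four-week delay forces no stop and is not counted toward the MTCA

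*Protocol*

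**What the plan says.** Protocol 4.7.1 lists the events after which no more treatment is given. Two items concern toxicity: "life-threatening toxicities outside of the DLT reporting period", and a DLT in dose escalation. The others are consent withdrawal and organ-dose limits. SAP 1.3.2.6 repeats the list. The term 'DLT reporting period' is not defined; it is read here as the assessment period of 4.7.1.1, from the first administration to the EOCT/ED visit.

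Section 4.7.1.1 enumerates the DLTs: named haematological events, raised AST/ALT with raised bilirubin, renal toxicity, GI events that do not settle within 48 hours, and death. The only other item that can reach a non-fatal event of an unlisted kind is toxicity "resulting in a treatment delay of more than four weeks due to either delayed recovery to baseline" or slow resolution. SAP 1.2 carries the same list.

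Other rules then key on DLTs:
- The MTCA (4.2.1.1) allows at most 33% of subjects to have a DLT in Cycles 1 and/or 2.
- Release of the next cohort (4.2.1.4): "If a DLT occurs after the first administration in cohort n, cohort n+1 will only be started after the second SRC".
- Use of the model (4.2.1.3): "if DLTs are reported, a statistical Bayesian modelling approach will be implemented to produce a more precise dose-DLT curve".
- The dose cap in Attachment 5, rule 3(a), applies "if there are two DLTs out of three, three DLTs out of five, or three DTLs out of six subjects" at a dose.
- The MTCA/MTSA set (12.1) keeps Cycle 2 completers and subjects who stopped because of a DLT. Section 4.7.1.3 lets other early discontinuations be replaced, except in Cohort 1.

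**The concern.** The same related life-threatening event has different consequences on either side of the EOCT visit. After it, treatment must end. Before it, if the event is off the list and recovers in time, nothing in the written rules ends treatment.

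The larger statistical issue is the count. The MTCA is the primary endpoint, and its toxicity part is a proportion of subjects with a DLT. Clinical discretion can protect the subject, but it does not put the event into the numerator. Withdrawal can even remove the subject from the denominator.

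Such events are foreseeable. Section 7.1.4.1 provides for severe infusion reactions and 8.2.4 for Holter monitoring at each dose, yet neither infusion reactions nor arrhythmias are on the list. Section 1.8 accepts that this first-in-human study may show effects that the animal work did not.

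**Working it through.** **Step 1. Follow one event through the rules.** Take an IMP-related, non-fatal, life-threatening event inside the window that is off the list and delays the next dose by no more than four weeks (the delay allowed in Attachment 1, Table 8).

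| Rule | Keys on | Effect of this event |
|---|---|---|
| Mandatory stop (4.7.1) | DLT, or life-threatening outside the window | None |
| 33% limit (4.2.1.1) | DLT | Adds 0 |
| Bayesian model (4.2.1.3, 19.5) | DLT | Not a trigger, not an input |
| Caps 3(a), 3(b) (19.5.2) | DLT count | Adds 0 |
| MTCA/MTSA set (12.1) | Cycle 2 completion or DLT stop | Excluded if withdrawn before the end of Cycle 2 |
| Replacement (4.7.1.3) | Non-DLT discontinuation | Allowed, except in Cohort 1 |

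Once the second dose has been given, no further core dose is planned outside Cohort 6. The delay item therefore has little force for Cycle 2 events.

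**Step 2. Rebuild the plan's model.** From 19.5.1:

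logit p = logit p0 + [(logit 0.33 − logit p0)/MTSA]·d1 + β·d2

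with p0 ~ beta(1, 9), MTSA ~ gamma(4, rate 0.5) and β ~ N(0, sd 0.25). Prior draws were weighted by the binomial likelihood.

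Check against the plan ("The prior probability distributions for the MTCA is summarised in Table 11"): for ≤5, 5–10, 10–15 and >15 GBq, Table 11 gives 32.5/24.6/15.7/27.2%. The rebuild, with the MTCA formula used as written, gives 31.6/25.7/15.7/27.0%, which is close.

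**Step 3. Apply assumed data.** These are illustrative counts, not event rates: 0/3 at 2×2.5 GBq, 0/3 at 2×4 GBq, then a cohort at 2×5.5 GBq.

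| Counted at 2×5.5 GBq | Mean DLT probability at 11 GBq | Pr(rate ≤33% at 11 GBq) | Written next level per cycle |
|---|---|---|---|
| 0/3 | 9.9% | 0.965 | 6.5 GBq |
| 1/3 (Cycle 2) | 21.9% | 0.792 | 6.5 GBq |
| 2/3 (both Cycle 2) | 37.1% | 0.456 | at most 5.5 GBq |
| 2/4 (one in Cycle 1, replaced) | 24.9% | 0.730 | 6.5 GBq |

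How the next level arises:
- With no DLT, the planned step is 11 + 2 = 13 GBq, i.e. 6.5 per cycle.
- With a DLT, the probability of being the MTSA is largest at 7.5 GBq in every row, so rule 3(c) limits the dose to 5.5 + 1 = 6.5.
- 2/3 meets cap 3(a), so the dose may not exceed 5.5. 2/4 meets neither cap.
- The 2/4 row follows Attachment 5: "Subjects with DLTs in Cycle 1 will be discontinued and replaced with a maximum of two replacements". The replacement is assumed to be DLT-free.

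Comparing the count as written with the count if the unlisted event were a DLT:
- No listed DLT plus one unlisted event in Cycle 2: 0/3 against 1/3. Next level unchanged.
- One listed DLT plus one unlisted event, both in Cycle 2: 1/3 against 2/3. Next level changes.
- One listed DLT in Cycle 2 plus one unlisted event in Cycle 1: 1/3 against 2/4. Next level unchanged.

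The posterior median MTCA is 13.1, 10.1 and 11.9 GBq for 1/3, 2/3 and 2/4. This is weak evidence: about 15–16% of the MTCA draws in the 1/3 and 2/4 cases are negative under the formula as written.

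**Step 4. Withdrawal and replacement.** Four subjects are treated: one has a listed DLT, one is withdrawn for the unlisted event and replaced, and two have no event. The 12.1 set counts 1/3 = 33%. Of those treated, 2/4 = 50% had a DLT or a life-threatening event.

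**The case against.** The strongest reply is that people, not the list, control re-dosing.
- The investigator may withdraw the subject (4.7.1), and a severe infusion reaction means stopping the infusion (7.1.4.1).
- The SRC and sponsor jointly decide on the second dosing cycle (4.2.1.4). On escalation, "The SRC will review all available data and make the final decision as to dose escalation, de-escalation, or cohort expansion" (12.2.8).
- The next cohort starts early only if, besides no DLT, every one of the three subjects can be given the full second dose. A subject no longer fit for full re-dosing blocks that release.
- Additional cycles need acceptable tolerability and sponsor agreement (4.2.1).
- A related Grade 2 or higher event cuts the increment to 2 GBq (4.2.1.3), and such events are tabulated (12.2.4).

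All of this stands, and it narrows the individual-stop gap mainly to the interval between Cycles 1 and 2. None of it adds the event to the DLT count.

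Attachment 7 also shows that the stop item came from an FDA request. A reader might infer that it took protection away inside the window. It did not: it extended stopping beyond the window, next to the existing DLT stop. For listed toxicities the in-window rule is the stricter one, since several Grade 3 events also force a stop.

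Finally, Attachment 5 describes simulation rules close to, but not identical with, the trial's conduct, and the SRC charter is not among the documents. It may already cover these events.

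**Conclusion.** The gap is real, narrow and worth closing. It concerns only related, non-fatal, life-threatening events that are off the list and recover within the permitted delay. For these, the written rules force no stop and leave the event out of the count that defines the primary endpoint. Withdrawal before the end of Cycle 2 takes the subject out of the evaluation altogether.

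The size is illustrative and no event rate is assumed. The estimated DLT probability rises in every modelled comparison when the event is counted, from 21.9% to 37.1% at 11 GBq in the largest. The written next level changes in one comparison only, 1/3 against 2/3 with both events in Cycle 2.

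Two stronger readings are tempting but unsupported. One is that subjects would be re-dosed after a life-threatening event: the discretionary controls make that far from automatic. The other is that escalation decisions would generally have differed: the SRC decides on all the data, and no changed SRC decision is shown. The conclusion assumes that the reporting period in 4.7.1 is the assessment period in 4.7.1.1, and that no unseen charter rule already applies.

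**What to change.** Use one threshold in both places, namely the 8.1.3 meaning of life-threatening (immediate risk of death).

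1. In Protocol 4.7.1 and SAP 1.3.2.6, replace the item with: 'IMP-related life-threatening toxicity (as defined in 8.1.3) at any time'.
2. In the DLT list (Protocol 4.7.1.1, synopsis, SAP 1.2), add: 'any other IMP-related life-threatening toxicity (as defined in 8.1.3), haematological or not'.

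Every subject stopped under item 1 inside the window is then a DLT and stays in the MTCA/MTSA set. A narrower DLT item, for instance non-haematological Grade 4 only, would leave some stopped subjects outside that set. Brief asymptomatic Grade 4 laboratory values remain acceptable.

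The cost is a protocol and SAP amendment and possibly a slightly lower MTCA. No new data are needed, because adverse events are already graded by CTCAE 5.0 and seriousness is already assessed. Attachment 7 shows that subjects had been treated before version 8.0, so events in those cohorts must be checked against the new item. That includes Cohort 2, whose data SAP 3.2.24 plans to use to support another study's starting dose. If the SRC charter already holds such a rule, move it into the protocol and SAP.
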